5.1 Inclusion Criteria

Patients are eligible to be included in the study only if all of the following criteria apply:

Informed Consent

1. Patient is capable of giving signed informed consent which includes compliance with the requirements and restrictions listed in the ICF and in this protocol.

Type of Patient and Disease Characteristics

- 2. Patient has a minimum life expectancy of 6 months.
- 3. Patient is 18 years or older at the time of signing the informed consent.
- 4. Histological or cytological confirmation of prostate cancer, BC, NSCLC and any other solid tumors.
- 5. Confirmed metastatic disease by imaging (e.g., bone scans, X-rays, ultrasound, computerized tomography [CT], magnetic resonance imaging [MRI]).
- 6. Documented disease progression (e.g., based on radiographic imaging, PSA or other clinical parameters) following first or later lines of anticancer systemic treatment.
- 7. Patient is eligible for low-dose EBRT for at least one lesion.
- 8. Patients with prior RT are eligible, only if there is no potential for field overlap between the prior RT and the planned RT.
- 9. For patients with BC or NSCLC: Patient must have at least one measurable lesion as per RECIST v1.1 (in Part 2 only).
- 10. Patient has Eastern Cooperative Oncology Group (ECOG) performance status of 0 to 2.
- 11. Adequate bone marrow function defined as:
 - Absolute neutrophil count $\geq 1.5 \times 10^9$ /L.
 - Platelet count $\geq 100 \times 10^9$ /L.
 - Hemoglobin \ge 9.0 g/dL (with or without transfusion).
- 12. Adequate renal function defined as:
 - Creatinine clearance as measured by the Cockcroft-Gault equation > 30 mL/min.

13. Adequate liver function defined as:

- Serum total bilirubin ≤ 1.5 × upper limit of normal (ULN; patients with confirmed Gilbert's syndrome may be included in the study).
- Aspartate aminotransferase (AST)/alanine aminotransferase (ALT) ≤ 2.5 × ULN (or ≤ 5 × ULN in patients with liver metastasis). Elevated alkaline phosphatase is not exclusionary if due to the presence of bone metastasis and liver function is otherwise considered adequate in the Investigator's judgement.

Metastatic Castration-resistant Prostate Cancer

- 14. Baseline testosterone levels \leq 14.4 ng/dL and ongoing medical castration must be maintained throughout the duration of the study.
- 15. Patient has evidence of symptomatic and/or progressive disease. Progressive disease is defined as any one of the following:

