8.1.3 Tumor Imaging Assessment

In this study, the preferred assessment of soft tissue lesions is CT or MRI scans using RECIST v1.1 criteria and the preferred assessment method for bone lesions is bone scan using PCWG-3.

Tumor imaging using RECIST v1.1 and PCWG-3 criteria will be performed during within 28 days prior to enrollment, every 8 weeks (\pm 7 days) from the first study dose administration up to Week 26, and every 12 weeks (\pm 7 days) thereafter until disease progression (as defined by RECIST v1.1 and PCWG-3 criteria), withdrawal of consent, initiation of new anticancer therapy or death. Tumor imaging should ideally be performed during the rest period before the start of the next treatment cycle.

- If a patient permanently discontinues the study drug due to disease progression according to RECIST v1.1 criteria, a tumor imaging and disease response assessment is not required.
- If a patient permanently discontinues the study drug due to clinical disease progression, a tumor imaging and disease response assessment does not need to be repeated if completed ≤ 28 days after the last dose of study drug.

For patients who permanently discontinue study drug for any reason other than confirmed disease progression, tumor imaging and disease response assessments will continue to be

performed every 12 weeks (\pm 7 days) for up to 12 months after the last dose of the study drug until disease progression, withdrawal of consent, initiation of new anticancer therapy, the patient is lost to follow-up or death, whichever comes first.

- If a patient meets disease progression during the follow-up period according to RECIST v1.1 criteria, a tumor imaging and disease response assessment is not required.
- If a patient meets clinical disease progression during the follow-up period, a tumor imaging and disease response assessment does not need to be repeated if completed ≤ 28 days after the date of clinical disease progression.

For patients who permanently discontinue the study drug or the follow-up period due to withdrawal of consent, the Investigator is to obtain tumor imaging and conduct a disease assessment at the time of the ED Visit or final Follow-up Visit if the patient agrees. A tumor imaging and disease response assessment does not need to be repeated if completed ≤ 28 days of the date of withdrawal of consent.

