8.1.7 Skeletal-related Events and Symptomatic Skeletal Events Assessment

Skeletal-related events and SSEs will be evaluated based on the patient's clinical history and examinations, including but not limited to incidence of fractures and pain. Assessments will be performed at each on-site study visit.

8.1.8 **Progression-free Survival**

Progression-free survival is defined as the duration of time from first dose administration to date of disease progression is objectively documented, including tumor progression, early discontinuation or death prior to data cut-off. Patients alive and progression-free at the time of data cut-off will be censored at the date last known alive. Progression-free survival will be assessed every 8 weeks (\pm 7 days) from the first dose administration up to Week 26, and every 12 weeks (\pm 7 days) thereafter until disease progression according to RECIST v1.1 criteria.

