Normal Tissue Constraints

In the context of this study, it is a requirement that the radiation oncologist will follow the QUANTEC Guidelines for normal tissue constraints when administering low-dose EBRT (20 Gy in 5 fractions or 8 Gy in 1 fraction) to metastatic lesions⁷. For 25 Gy in 5 fractions, the dosing guidance from the AAPM Task Force Group 101 has to be followed². This study will be excluding all patients who have central nervous system involvement; therefore, the CNS tissue tolerances, with the exception of spinal cord exposure, will not be included in the guidance on normal tissue dose constraints as set out below. These constraints are for EBRT at low dose and for standard fractionation.

Tissue / Organ	Tissue radiation dose constraints (maximum radiation dose)
Spinal cord	23 Gy
Retina	< 50 Gy
Cochlea	\leq 45 Gy
Single parotid gland sparing	< 20 Gy
Irradiation to 2 parotid glands	< 25 Gy (spread across 2 glands)
Mandible	\leq 70 Gy
Pharyngeal constrictors	< 50 Gy
Larynx	< 44 Gy
Brachial plexus	< 60 Gy
Lung	20 Gy
Oesophagus	< 34 Gy
Heart	< 26 Gy
Liver	\leq 28 Gy
Kidney	< 18 Gy per kidney
Stomach	< 50Gy
Small bowel (irradiation to less than one-third)	50 Gy
Rectum	< 27 Gy
Skin	40 Gy
Bladder	< 65 Gy
Femoral head	< 52 Gy

Equipment

Radiation delivery equipment needs to have undergone appropriate dosimetry calibration using an acceptable phantom to ensure that the correct treatment beam energies are being generated, correct alignment between on-board imaging and treatment isocenter, and accurate motion of the treatment couch. This calibration needs to be performed at a minimum of once every 3-4 years to ensure acceptable quality control as per treatment site SOPs.

Treatment Dose Interruptions

Treatment dose interruption for the single fraction Gy regimen is not applicable.

For a patient who will be receiving 20/25 Gy over 5 fractions, dose interruption must occur if a patient experiences a Grade 3 or higher adverse reaction in any organ/tissue that is due to the radiation therapy. The fractionated therapy can only resume once the adverse reaction has recovered or stabilized back to Grade 2 or less.

Patients with tumors involving the central nervous system are excluded from this study. It is anticipated that over 50% of patients recruited into this study will require symptomatic low-dose EBRT to bony metastases, with involvement of other soft tissue organ lesions for the rest of the patients.

References

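### Sections 8.1.8 and 8.1.3 conflict on whether bone-scan progression is a PFS event in mCRPC, and either literal reading of 8.1.8 biases Arm 1 PFS

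*Combined protocol and SAP*

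**What the plan says.** Three sentences of Section 8.1.8 (Progression-free Survival) matter.

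- The event sentence runs time from first dose until "disease progression is objectively documented, including tumor progression, early discontinuation or death prior to data cut-off". It names no response criterion.
- The censoring sentence reads: "Patients alive and progression-free at the time of data cut-off will be censored at the date last known alive".
- The schedule sentence has assessments every 8 weeks to Week 26 and every 12 weeks "thereafter until disease progression according to RECIST v1.1 criteria".

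Section 8.1.3 (Tumor Imaging Assessment) uses the same intervals but a wider end point: "thereafter until disease progression (as defined by RECIST v1.1 and PCWG-3 criteria), withdrawal of consent, initiation of new anticancer therapy or death". Section 10.5 (Appendix 5) applies RECIST v1.1 to soft-tissue lesions and PCWG-3 to bone lesions, the latter in mCRPC only.

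Section 9.4.7.2 adds only that PFS is estimated by Kaplan-Meier. It gives no event or censoring rules. Section 9.4 leaves further detail to a SAP that is to be finalized before database lock.

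**The concern.** Bone-only progression is foreseeable in Arm 1, which plans 40 mCRPC patients. Section 5.1 requires measurable disease only elsewhere: "For patients with BC or NSCLC: Patient must have at least one measurable lesion as per RECIST v1.1 (in Part 2 only". The same section lets mCRPC patients enter on radiographic progression in bone. Appendix 10 anticipates, across all tumor types, that "over 50% of patients recruited into this study will require symptomatic low-dose EBRT to bony metastases".

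In such a patient the bone scan is read by PCWG-3, but the only criterion that Section 8.1.8 names is RECIST v1.1. Two programmers could follow the same section and report different Arm 1 medians. The mCRPC patients in Part 1 are affected in the same way. No hypothesis is tested (Section 9.1), and Section 9.2 says that Part 2 was sized for estimation and for seeing a signal of efficacy. The estimate is therefore the result, and its definition has to be fixed in advance.

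**Working it through.** The plan states no PFS median or event count, so there is no figure to reproduce. The check has two steps.

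**Step 1: the status of a patient with bone-scan progression only**

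| Text | Consequence |
|---|---|
| 8.1.8, schedule sentence | RECIST v1.1 only; with 10.5, no bone-scan component |
| 8.1.8, event sentence | Can be an event, either as objectively documented progression or as early discontinuation if the drug is stopped |
| 8.1.8, censoring sentence | If not an event, censored at date last known alive. The Schedule of Activities (Table 1-1, note b) continues survival contact every 3 months after progression, so this date can be well after the bone progression |
| 8.1.3 | Has progressed, by PCWG-3 |

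No section settles which of these governs.

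**Step 2: how far the readings differ**

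All inputs are assumptions: exponential times, a true median of 6 months, a share s of first progressions seen only on bone scan (20%, 40%, 60%), and a share d of exits that are stops for toxicity or patient choice (10%, 20%).

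*Reading A: RECIST only, bone progressors censored at bone progression.* The event hazard is (1 − s) times the true hazard, so the median is 6/(1 − s):
- s = 20%: 6/0.8 = 7.5 months
- s = 40%: 6/0.6 = 10.0 months
- s = 60%: 6/0.4 = 15.0 months

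*Reading A with the censoring sentence applied.* Bone progressors stay at risk to the date last known alive, or become events at death. Simulation (200,000 patients per scenario, 18-month cut-off, assumed median survival of 12 months after progression) gives 7.8, 10.3 and 13.9 months for the same three shares.

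*Reading B: the literal event sentence.* Bone progression and every early discontinuation are events. If non-progression stops are a share d of exits, the total hazard is the true hazard divided by (1 − d), and the median is 6(1 − d):
- d = 10%: 6 × 0.9 = 5.4 months
- d = 20%: 6 × 0.8 = 4.8 months

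*Mixed reading: other discontinuations are events, bone progression is censored.* The median is 6/[(1 − s) + d/(1 − d)]:
- s = 20%, d = 10%: 6/(0.8 + 0.111) = 6.6 months
- s = 20%, d = 20%: 6/(0.8 + 0.25) = 5.7 months
- s = 60%, d = 20%: 6/(0.4 + 0.25) = 9.2 months

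So this reading can err in either direction.

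With bone progression counted and non-progression stops not counted, the estimate returns the assumed 6.0 months.

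**The case against.** The strongest reply is that the schedule sentence sets only how often and how long PFS is assessed, while the event sentence governs and is not limited to RECIST. A patient with a positive bone scan is then an event as objectively documented progression. It also follows that such a patient is not progression-free, so the rule on the date last known alive never applies. This is a fair reading, and it defeats any flat statement that bone progression is not an event. It does not remove the contradiction: the only criterion named for PFS still excludes bone, whereas the protocol names both criteria where it means both, as for overall response in Table 3-1. The other route, early discontinuation, captures the bone progressor only by counting stops for toxicity or patient choice as progression too. That is a second defect.

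A reader might also infer the following, which the documents do not support:

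- *That imaging and treatment stop at either criterion.* Section 8.1.3 joins the two criteria with an and. Section 7.1.1 ties stopping study drug to disease progression without naming either criterion.
- *That follow-up ends at bone progression.* Survival contact continues.
- *That over half of Arm 1 will progress in bone only.* The Appendix 10 figure concerns lesions to be irradiated across all tumor types, not the site of first progression in mCRPC.
- *That carrying patients to the date last known alive always makes the inflation worse.* At s = 60% it gives 13.9 months, against 15.0 for censoring at bone progression.

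Finally, PFS is one of several secondary endpoints and the Arm 1 primary endpoint is PSA response. That stands, and it limits the severity.

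**Conclusion.** The status of bone-scan progression as a PFS event in mCRPC is contradictory between Sections 8.1.8, 8.1.3 and 10.5. It is tempting to conclude that Arm 1 PFS is overstated. That holds on the RECIST-only reading, but the literal event sentence gives the opposite bias, so the documents do not establish a direction.

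For an assumed true median of 6 months, the RECIST-only reading gives 7.5 to 15 months by the simple formula, and the literal reading gives 4.8 to 5.4 months. At s = 40% and d = 10% the two readings give 10.0 and 5.4 months, a ratio of about 1.9. The existence of the conflict rests on the text alone. Its size rests on the assumed median and shares, none of which the documents supply.

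Severity: should-fix. No sample size, error rate, power or primary endpoint depends on PFS.

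**What to change.** In Sections 8.1.8 and 9.4.7.2, before database lock:

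1. For mCRPC, define PFS as time from first dose to the earliest of RECIST v1.1 soft-tissue progression, PCWG-3 bone progression or death from any cause.
2. For BC and NSCLC, use RECIST v1.1 progression or death. Other Part 1 tumor types would follow the same rule, since Section 10.5 applies PCWG-3 bone criteria to mCRPC only.
3. Remove early discontinuation as a PFS event. Section 8.1.3 already provides for observing these patients: if the drug is stopped for a reason other than confirmed progression, scans go on at 12-week intervals for up to a year after the last dose.
4. Censor patients without an event at the last evaluable tumor assessment, not at the date last known alive.
5. Word the end of imaging in Section 8.1.3 to match this definition.

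Bone scans are already in the schedule, so no new procedure is needed. The cost is a short text change and a small amount of analysis work. The reported Arm 1 PFS may move in either direction: counting bone progression shortens it relative to the RECIST-only reading, and removing early discontinuation lengthens it relative to the literal one.

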8.1.9 Overall Survival

Overall survival is defined as time from the date of first dose administration to date of death due to any cause. Patients alive at the time of data cut-off will be censored at date last known alive.

8.1.10 Overall or Objective Response Rate

Response rate is defined as the proportion of patients who have confirmed CR or PR by objective disease progression RECIST v1.1, as assessed by the Investigator/local radiologist. Overall or ORR will be assessed every 8 weeks (\pm 7 days) from the first dose administration up to Week 26, and every 12 weeks (\pm 7 days) thereafter until disease progression.

Complete response is defined when all target lesions present at baseline have disappeared (with the exception of lymph nodes which must be < 10 mm to be considered nonpathological) and no new lesions have developed since baseline. A visit response of PR is defined when the sum of diameters of the target lesions has decreased by 30% or more compared to baseline (with no evidence of progression).

8.2 Safety Assessments

8.2.1 Administrative Procedures

8.2.1.1 Informed Consent

Informed consent must be documented according to Section 10.1.3.

8.2.1.2 Participant Identification Card

All patients will be given a patient identification card identifying them as participants in a research study. The card will contain study site contact information (including direct telephone numbers) to be used in the event of an emergency. The Investigator or qualified designee will provide the patient with a patient identification card immediately after the patient provides written informed consent.

The patient identification card also contains contact information so that a healthcare provider can obtain information about study drug in emergency situations where the Investigator is not available. At the time of enrollment/study drug allocation, site personnel will add the study drug dosage to the patient identification card.

8.2.2 Screening and Eligibility Assessments

8.2.2.1 Eligibility Criteria

All inclusion and exclusion criteria (Section 5.1 and Section 5.2) will be reviewed by the Investigator or designee to ensure that the patient qualifies for the study. Review of eligibility criteria will be done at Screening and at the Day -1 visit.

8.2.2.2 Participant Demographics and Baseline Characteristics

Demographic data will be collected including age (at the day of Screening), gender, race, ethnicity and baseline characteristics (e.g., tobacco and smoking history, alcohol consumption history) as allowed by the local regulations.

8.2.2.3 Medical History

A medical history will be obtained by the Investigator or qualified designee at Screening. The medical history will collect all active and chronic conditions from each patient. Gleason score will be collected as part of the medical history for patients with mCRPC only. Details regarding the disease for which the patient has enrolled in this study will be recorded separately and not

listed as medical history. If the patient has data available from any historical genetic assays conducted to identify genetic variations, this will also be collected (all patients).

8.2.2.4 **Prior and Concomitant Medications Review**

The Investigator or qualified designee will review prior medication use and record prior medications taken by the patient within 30 days prior to the Screening Visit.

The Investigator or qualified designee will record medication, if any, taken by the patient during the study through the last visit. Concomitant medications will be recorded for 30 days after the last dose of study drug (or longer if related to an SAE).

8.2.2.4.1 Permitted Medications

Analgesic agents, ADT, bisphosphonates and denosumab are allowed to be used during the study. The Investigator or qualified designee will review the use of analgesic agents taken by the patient as part of the concomitant medications review (see SoA [Table 1-1 (Parts 1 and 2)]).

Anti-microbial agents to control infections (e.g., urinary tract infection) are allowed as per SOC guidelines.

Topical hydrocortisone-containing hemorrhoid cream/ointment and/or cutaneous cream is allowed for the treatment of a perineal and/or anal rash and can be administered straight after study drug administration, and as frequently as required as per institution.

The use of a small amount of water-soluble lubricant is advised before rectal administration. No oil- or wax-based lubricants should be used during rectal administration.

8.2.2.4.2 Prohibited Medication

The following medications and therapies are not allowed during the study:

- Any concomitant chemotherapy.
- Oral or parenteral glucocorticoids and herbs known to alter PSA levels.
- Other investigational agents.
- Inducers (phenobarbital) and inhibitors (valproic acid, probenecid, atazanavir, gemfibrozil, indinavir) of phase 2 drug metabolizing enzymes are prohibited within 14 days prior to first dose of NOX66 and the rest of the study.

- Based on *in vitro* data, idronoxil may inhibit the activity of cytochrome P450 (CYP) 2C8, CYP2C9, CYP2C19 and CYP3A4 enzymes in human microsomes in a range of 0.457 to 3000 μM and concomitant medication that is metabolized by these enzymes should be used with caution.
- The use of inhibitors of uridine 5'-diphospho-glucuronosyltransferase (UGT) enzymes should be avoided.
- Soya contains a high proportion of isoflavones which may interfere with the bioanalytical assay used for detection of idronoxil (active substance), itself an isoflavone derivative, in plasma and urine samples, thus within 2 days prior to NOX66 administration and for the entire duration of the first cycle of the study, patients must be on a soya free diet. The following types of foods are prohibited: edamame, meat alternatives, miso, soymilk, soy nuts, soy sauce (tamari, shoyu and teriyaki), tempeh, and textured soy protein. Trace or very small amounts of soy in foods are permitted.

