At a minimum, imaging of the chest, abdomen and pelvis should be performed using consistent imaging modality (computerized tomography [CT] or magnetic resonance imaging [MRI]). As far as possible, the same imaging method should be used for the patient throughout the study.

- W. Questionnaire to be completed at Screening, Day 1 of Cycle 3, Day 1 of Cycle 5 followed by every 4 cycles thereafter (e.g., Cycle 9, Cycle 13 etc.) and at the EOT/ED Visit. Questionnaire to be completed prior to performing any other study visit assessments on the day of the visit.
- x Questionnaire to be completed on Day 2 of Cycle 1, Day 1 of Cycle 3 and at the EOT/ED Visit. Questionnaire to be completed prior to performing any other study visit assessments on the day of the visit (excluding predose clinical laboratory assessment for Cycle 1 Day 1 which may be completed within 3 days prior to Day 1).
- ^{y.} May be an in-person visit or a phone call. Only applicable to patients who have met disease progression.
- ^{z.} Pharmacokinetic samples are to be obtained on Days 1, 2, 6, 14 and 15 of Cycle 1, and Days 1 and 8 of Cycles 2 and 3. See PK sampling schedule in Table 1-3. For Part 2, PK sampling will only be performed for the first 10 patients enrolled for each tumor group (mCRPC, breast cancer or non-small-cell lung cancer).
- aa. Pharmacodynamic blood samples to be collected at Screening or Cycle 1 on Days 1 and 15, prior to dosing on Day 1 of Cycle 3 (during the rest period after patients have completed 7-days of NOX66 treatment in Cycle 2, or predose on Day 1 of Cycle 3) and at the EOT/ED Visit. See PD sampling schedule in Table 1-4.
- ^{bb.} Patients will be asked whether they are willing to provide both archival and fresh tissue biopsy samples OR only fresh tissue biopsy if they do not have archival tissue samples. Available archival tissue samples will only be requested if a fresh tissue biopsy is collected after Cycle 3. Provision of a fresh biopsy sample and/or an archival tissue sample is optional. See Table 1-5.

- ^{cc.} On days when study drug and EBRT are to be administered, it is advisable that NOX66 is given at least 1 hour prior to EBRT. Twice daily of NOX66 dosing should occur at least 10 hours apart. Where 2 suppositories are administered per dosing, each suppository will be administered at least 5 minutes apart.

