9.4.7.3 Pharmacokinetic Evaluation

Plasma samples will be assayed for idronoxil and up to 7 selected metabolites by validated LC-MS/MS. Individual plasma concentration-time data and plasma PK parameters will be summarized using descriptive statistics by treatment day and sampling time for idronoxil and the 7 detectable metabolites (GIS/SIG, IG, GI, IS, SI, SIS, and GIG). Plasma PK parameters will be determined by noncompartmental analysis for idronoxil and selected metabolites (SI, IS, GI, IG, SIG/GIS, GIG, SIS) and will be summarized by dose and treatment day.

The following PK parameters will be estimated for idronoxil and the selected metabolites following the morning dose on Days 1, 6 and 14 of Cycle 1, as data permit: C_{max} , C_{min} (predose), T_{max} , $AUC_{(0-t)}$, $AUC_{(0-6)}$, $AUC_{(0-12)}$, $AUC_{(0-inf)}$ and $t_{\frac{1}{2}}$. Details of the analyses will be included in the SAP.

Dose proportionality will be assessed using the power model for C_{max} , $AUC_{(0-t)}$, $AUC_{(0-inf)}$, $AUC_{(0-6)}$, and $AUC_{(0-12)}$ on Days 1, 6 and 14 of Cycle 1 for the parent compound.

If data permits, accumulation ratios will be calculated for parent compound and selected metabolites for C_{max} , C_{min} , $AUC_{(0-t)}$, $AUC_{(0-inf)}$, $AUC_{(0-6)}$, and $AUC_{(0-12)}$ for Days 6 and 14 of Cycle 1 (e.g., Day 14/Day 1 and Day 6/Day 1) and Day 8 of Cycles 2 and 3.

The metabolite to parent ratios will be calculated (as data permit) for Days 1, 6 and 14 of Cycle 1, for $AUC_{(0-t)}$, $AUC_{(0-inf)}$, $AUC_{(0-6)}$, and $AUC_{(0-12)}$ and for single time points on Day 1 of Cycles 2 and 3.

Concentration and PK parameter data will be listed, summarized and plotted. Details of these analyses will be included in the SAP.

There are no formal PK parameters for concentration data from Cycles 2 and 3 because these are single time points. However, metabolite to parent ratios will be explored.

Exploratory analyses of the relationship between plasma concentrations of parent drug and selected metabolites and/or PK parameters and AEs or PD biomarkers may be assessed by graphical methods and special summary tables. Exposure-response relationship may also be explored.

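### The soya-free diet that protects the idronoxil assay ends with Cycle 1, while a few PK samples used for later-cycle ratios are taken in Cycles 2 and 3

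*Combined protocol and SAP*

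**What the plan says.** Section 8.2.2.4.2 gives its reason first: "Soya contains a high proportion of isoflavones which may interfere with the bioanalytical assay used for detection of idronoxil". It then sets the window of the diet: "for the entire duration of the first cycle of the study, patients must be on a soya free diet". The lead-in to that window is worded as "within 2 days prior to NOX66 administration". The control is not absolute even inside that window: "Trace or very small amounts of soy in foods are permitted". No other section mentions soya.

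PK sampling goes on after Cycle 1. Footnote z to Table 1-1 adds to the Cycle 1 days "and Days 1 and 8 of Cycles 2 and 3". Table 1-3 limits the Cycle 3 samples to Part 2, where Section 8.5 limits PK sampling to the first 10 patients in each of three tumor groups.

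The later samples have a stated use. Section 9.4.7.3 plans accumulation ratios, if the data allow, for Days 6 and 14 of Cycle 1 "and Day 8 of Cycles 2 and 3". It plans metabolite-to-parent ratios at single time points on Day 1 of Cycles 2 and 3. It also says that no formal PK parameters come from Cycles 2 and 3, and then adds: "However, metabolite to parent ratios will be explored".

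**The concern.** The protection stops while samples run on the same assay are still being drawn, and the protocol does not say why the later ones need less of it.

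An accumulation ratio sets a later concentration against one from Cycle 1. If the earlier one is measured under diet control and the later one is not, any interference does not cancel. It could be read as accumulation or as loss of exposure. In the metabolite-to-parent ratio it could be read as a change in metabolism. These sparse samples are the only exposure data beyond Cycle 1 for a drug that is given until progression.

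An affected sample could not be recognized afterwards. The diary described in Section 6.4 records dosing, the Schedule of Activities has no dietary item, and Table 1-3 lets the Day 8 samples be collected at home.

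**Working it through.** **Inputs.** Sample times and part restrictions come from Table 1-3 and its footnotes. Cycle lengths (21 days for Cycle 1, 14 days after that) come from Section 4.1. The diet window is in Section 8.2.2.4.2, the stated maximum of 31 samples in Section 8.5, and the Part 1 size (up to 30) in Section 9.2.

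**1. The plan's own figure.** Counting every cell of Table 1-3 over both parts:

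C1D1 9 + C1D2 1 + C1D6 7 + C1D14 7 + C1D15 1 + C2D1 2 + C2D8 1 + C3D1 2 + C3D8 1 = 31.

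This matches Section 8.5. It is an upper bound that no single patient reaches once the footnotes apply (8 h and 12 h samples in Part 1 only, Cycle 3 in Part 2 only):

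- Part 1: 9 + 1 + 7 + 7 + 1 = 25 in Cycle 1, plus 2 + 1 = 3 in Cycle 2, total 28.
- Part 2 PK patients: 7 + 1 + 7 + 7 + 1 = 23 in Cycle 1, plus 3 in Cycle 2 and 3 in Cycle 3, total 29.

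**2. Where the later samples fall.** With no dose delay, Cycle 2 Day d is study day 21 + d and Cycle 3 Day d is study day 35 + d. The last required diet day is Day 21.

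| Sample day | Study day | Days after Day 21 | Samples | Part |
|---|---|---|---|---|
| C2D1 | 22 | 1 | 2 (predose, 2 h) | both |
| C2D8 | 29 | 8 | 1 | both |
| C3D1 | 36 | 15 | 2 (predose, 2 h) | Part 2 |
| C3D8 | 43 | 22 | 1 | Part 2 |

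**3. Samples outside the window, natural reading.**

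- Part 1: 3/28 = 10.7%. Part 2: 6/29 = 20.7%.
- The C2D1 predose sample is taken the morning after the diet ends. A compliant patient has then been soya-free for far longer than the protocol's own 2-day lead-in, so this sample is protected in practice. Without it: Part 1, 2/28 = 7.1%; Part 2, 5/29 = 17.2%.
- Trial-wide upper bound, if every PK patient reaches these visits: 30 × 3 + 30 × 6 = 270 samples. Without C2D1 predose it is 30 × 2 + 30 × 5 = 210.

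**4. Other readings of the 2-day phrase.**

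- Before the first dose of each cycle: the Day 1 predose samples are covered. The Day 8 samples are not: 1/28 = 3.6% in Part 1 and 2/29 = 6.9% in Part 2.
- Before every administration: dosing Days 1 to 7 are covered as well. Only the roughly 12 hours between the Day 7 evening dose and each Day 8 sample stay open.

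**5. Effect on the ratios.** Suppose interference changes a later-cycle concentration by a fraction f and Cycle 1 is clean. An accumulation ratio is then multiplied by (1 + f). If metabolite and parent are changed by fractions g and f, their ratio is multiplied by (1 + g)/(1 + f), which cancels only when g = f. The documents give neither the size nor the sign of f or g.

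**The case against.** The strongest answer is that little depends on these samples. Cmax, AUC, half-life and dose proportionality come from Cycle 1 Days 1, 6 and 14, all inside the diet window. The accumulation ratios are conditional on the data, and a single Day 8 sample about 12 hours after the last dose supports a trough comparison at most. No DLT rule or primary endpoint uses later-cycle PK. All of this stands and sets the limits of the point.

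Second, the wording may reach further than it seems. The soya bullet does not say first dose, whereas the bullet on phase 2 enzyme inducers and inhibitors does. A per-administration reading would close much of the gap. This stands in part. However, the phrase is joined to a limit of one cycle, and the enzyme bullet explicitly carries its ban through the remaining study where that was meant. A lead-in to first dosing is the more natural reading. If sites could reasonably differ, the sentence needs clarifying in any case.

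Third, the protocol says only that soya may interfere, and it describes the assay as validated. That is fair: this is a risk and not a shown bias. Validation does not dispose of it, because the protocol still judged the diet necessary in Cycle 1.

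A reader might infer that all later-cycle exposure data are unprotected, or that the secondary exposure objective is compromised. The documents support neither. The Cycle 2 Day 1 predose sample is in practice covered, and the 2-hour sample that day is at risk only if soya is eaten that morning. Part 1 has no Cycle 3 samples. Table 3-1 states the exposure objective without a later-cycle component.

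**Conclusion.** The mismatch between the diet window and the PK schedule is real, and the consequence is limited. On the natural reading, 2 of 28 samples per Part 1 patient and 5 of 29 per Part 2 PK patient are drawn with no effective soya restriction. What is at risk is the descriptive comparison of later cycles with Cycle 1, through the accumulation and metabolite-to-parent ratios.

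This rests on three assumptions: the 2-day phrase refers to the first dose, cycles run without delay, and patients comply with the Cycle 1 diet. Confidence is high in the schedule mismatch. No statement about the size or direction of interference can be made from the documents. The point is a cheap improvement and is best made before the samples are drawn, because without diet records an exposed sample cannot be identified later.

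**What to change.** Reword the soya sentence in Section 8.2.2.4.2 so that it clearly covers every scheduled PK sample, in one of two ways:

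- run the restriction to the patient's last PK sample, which is Cycle 2 Day 8 in Part 1 and Cycle 3 Day 8 for Part 2 PK patients; or
- keep the Cycle 1 restriction and apply the existing 2-day lead-in before each Cycle 2 and Cycle 3 PK sample.

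Under either option, record soya intake at those samples, including Day 8 samples collected at home, and state in Section 9.4.7.3 that exposed samples will be flagged in the ratio summaries. If the sponsor holds assay selectivity data showing that dietary isoflavones do not matter, saying so would serve instead.

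The first option adds 29 − 21 = 8 diet days in Part 1 and 43 − 21 = 22 in Part 2. The second adds about 2 days before each later PK visit not already covered by the Cycle 1 diet. The extension need apply only to patients who give PK samples. No visits or blood samples are added. The change needs a minor protocol amendment with the approvals in Section 10.1.11, revised patient instructions, and possibly a consent form update.
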